### **8.5.3 Pharmacokinetics**

A mixed effects modeling approach will be taken in order to analyze the complete PK data from the study. Quality of individual fits to the dataset will be assessed and if the fits are apparently unbiased, the model derived population pharmacokinetic model parameter mean and inter-individual variance-covariance matrices of parameters such as CL (clearance), V

(apparent volume of distribution),  $k_a$  (first-order absorption rate constant) and withinindividual variance will be estimated. In addition, posthoc estimates of the same parameters, i.e. CL, and V will be reported for each individual.

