### 3 Investigational plan

#### 3.1 Study design

The study will be conducted as an exploratory open-label pilot trial. There will be only one treatment arm. The improvement will be evaluated in comparison to the findings recorded at the baseline.

Figure 3-1 Study design

Approximately 10 subjects aged 18 to 60 years, who sign an informed consent and meet all inclusion and exclusion criteria in the screening period will enter into the study. The first dose of canakinumab will be administered as 300 mg IV.

At the end of the first month, an analysis will be conducted to assess the complete, partial, and non-responders to canakinumab treatment by physician.

Partial responders will be able to take the 2nd canakinumab dose as 300 mg IV infusion at the first month then will continue the canakinumab treatment with 150 mg IV infusions at monthly intervals for 4 times. The complete responders will continue the canakinumab treatment with 150 mg IV infusions at monthly intervals for 5 times. Non-responder or deteriorating patients will be dropped from the study at the first month evaluations.

At month 6, the patients will be able to switch to SC injections or continue as IV infusions of 150 mg canakinumab for additional 6 monthly administrations. Non-responder or deteriorating patients will be dropped from the study at the first month evaluations.

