## 5 Treatment

Treatment Arm	# of Patients Entered Treatment	Type of Study Drug	Compound	Min Dose	Max Dose	Frequency	Admin. Route	Generic Acceptable?
Canakinumab	10	Investigational	ACZ	150 mg	300 mg	Monthly	IV (SC after month 6)	-

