### 5.10.7 Pharmacokinetics

All blood samples will be taken by either direct venipuncture or an indwelling cannula inserted in a forearm vein. It is important to note that the volume of blood sampling will be adapted to the age of the child according to clinical practice at the investigator site. For each scheduled PK sample, 2 mL of blood will be drawn into a plain barrier tube to obtain 1 ml serum. The sample will be allowed to clot during 45 minutes at room temperature. The serum will be obtained by centrifugation at approximately 2500 g for 10 minutes. The sample will be split into two aliquots to be transferred into polypropylene screw-cap tubes. Serum tubes will be frozen within 90 min of venipuncture and kept at  $\leq -18^{\circ}\text{C}$  pending analysis. One of the two serum samples is to be kept at the study site as a backup while the other one will be shipped to the analytical center.

Time points for canakinumab PK sample collection at Visits:

- Day 0 (Visit 1)
- Day 7 (Visit 2)
- Day 30 (Visit 4); pre-dose
- Day 60 (Visit 5); pre-dose
- Day 90 (Visit 6) pre-dose
- Day 180(Visit 9) pre-dose
- Day 240(Visit 11) pre-dose
- Day 360 (Visit 15) pre-dose

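### Section 8.5.3 plans a population absorption rate constant with between-patient variance, but at most two pre-dose troughs per patient can follow a subcutaneous dose

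*Combined protocol and SAP*

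**What the plan says.** Section 8.5.3 plans a mixed-effects model for all the PK data. Subject to a check of the individual fits ("if the fits are apparently unbiased"), it will give population means and "inter-individual variance-covariance matrices of parameters such as CL (clearance), V", continuing through ka to "first-order absorption rate constant) and withinindividual variance will be estimated". Individual values are narrower: "posthoc estimates of the same parameters, i.e. CL, and V will be reported for each individual".

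The treatment table in Section 5 gives the route as "IV (SC after month 6"). Section 3.1 makes the switch optional: "At month 6, the patients will be able to switch to SC injections or continue as IV infusions of 150 mg canakinumab". Section 5.5.5 places it at the end of month 6.

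Section 5.10.7 schedules serum samples on Days 0, 7, 30, 60, 90, 180, 240 and 360, all pre-dose from Day 30 on. The last two are "Day 240(Visit 11) pre-dose" and "Day 360 (Visit 15) pre-dose". The documents name no bioavailability parameter, no external value for ka and no pooling with other studies.

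**The concern.** IV data carry no information on absorption, so ka can be learned only from samples that follow an SC dose, and best from samples taken while the drug is still being absorbed. No such sample is scheduled. What remains is one or two troughs about a month after a dose, in those patients who happen to switch. A trough responds to ka and to bioavailability in the same way, as a modest vertical shift.

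At stake is whether the report presents a population ka and a between-patient variance that come mainly from starting values or noise. The plan's only safeguard is that the fits look unbiased. That would not reveal the problem, because many values of ka fit troughs equally well.

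**Working it through.** **1. Reproduce the sampling count.** The list in Section 5.10.7, the PK row of the assessment schedule and Table 13-1 all give the same 8 collections.

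**2. Count the samples that can follow an SC dose.** The earliest SC dose is on Day 180. The Day 180 sample is pre-dose, so it reflects IV dosing only. Days 240 and 360 remain: 2 × 10 = 20 samples if all 10 patients switch and stay, and 0 if none do. Non-responders leave at month 1 (Section 3.1), so 20 is a ceiling. Each trough falls about 30 days after the last dose. With the ±7-day visit window (Section 5.7) the extremes are 30 - 14 = 16 and 30 + 14 = 44 days.

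**3. How far ka moves a trough.** Assumptions, not in the documents: one compartment, half-life 15-30 days, ka 0.15-2.0 per day with 0.3 as reference. At SC steady state with a 30-day interval, the trough is proportional to

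F × ka/(ka - ke) × [e^(-30ke)/(1 - e^(-30ke)) - e^(-30ka)/(1 - e^(-30ka))], with ke = ln 2 / half-life.

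Half-life 15 days (ke = 0.0462; first term in brackets 0.25/0.75 = 0.3333), F = 1:
- ka 0.15: 1.4452 × (0.3333 - 0.0112) = 0.4655
- ka 0.3: 1.1821 × (0.3333 - 0.0001) = 0.3939
- ka 2.0: 1.0237 × 0.3333 = 0.3412

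Relative to ka 0.3 this is +18.2% and -13.4%. At a 30-day half-life the values are 1.1688, 1.0833 and 1.0117, that is +7.9% and -6.6%.

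**4. Use the actual schedule.** Day 240 follows only two SC doses (Days 180 and 210), so it is not at SC steady state. Example: half-life 15 days, F = 0.7 (assumed), complete-responder dosing, in units of 150 mg/V, where each 30 days multiplies by 0.25.
- IV carry-over: 0.25³ + 0.25⁴ + 0.25⁵ + 0.25⁶ + 0.25⁷ + 2 × 0.25⁸ = 0.0208
- SC part at ka 0.3: 0.7 × 1.1821 × (0.25 + 0.0625 - 0.0001) = 0.2585; total 0.2793
- Total at ka 0.15: 0.3256 (+16.6%); at ka 2.0: 0.2448 (-12.4%)
- 20% change in F: 0.2 × 0.2585/0.2793 = 18.5%

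| Sample, half-life (F = 0.7) | ka 0.15 | ka 2.0 | F ± 20% |
|---|---|---|---|
| Day 240, 15 d | +16.6% | -12.4% | ± 18.5% |
| Day 240, 30 d | +5.2% | -4.6% | ± 13.9% |
| Day 360, 15 d | +18.2% | -13.4% | ± 20.0% |
| Day 360, 30 d | +7.7% | -6.5% | ± 19.6% |

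A 20% change in bioavailability is thus as large as, or larger than, the shift from either end of a 13-fold range of ka (2.0/0.15 = 13.3).

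**5. Why the variance fails.** With the second exponential negligible, the proportional change in a trough per proportional change in ka is about -ke/(ka - ke). At ka 0.3 and a 15-day half-life this is 0.0462/0.2538 = 0.18. An assumed 30% between-patient SD in ka then moves the trough by 0.30 × 0.18, or about 5%, against an assumed residual SD of 20%.

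**6. Expected precision.** First-order population information matrix on the protocol's doses and days, best case (all 10 patients switch). Assumptions: half-life 10-30 days, ka 0.1-1 per day, F 0.7, V 6 L, between-patient SD 30%, residual SD 20%. Entries are relative standard errors (RSE).

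| Quantity | RSE |
|---|---|
| Mean ka, F estimated, exact visit days | at least 190%; correlation with F 0.95-1.00; singular at ka 1 |
| Mean ka, F estimated, visit-window scatter | 34-96% at ka 0.1; 286-1107% at ka 0.3; singular or nearly so at ka 1 |
| Mean ka, F known | about 16-312% |
| Between-patient variance of ka | at least 118% in every scenario |
| CL and V | about 10-12% |

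Above ka 1 the ratio in step 5 shrinks further, so the troughs say still less.

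**7. What a trough ratio can show.** In the units of step 4 the Day 180 IV trough is 0.25 + 0.25² + 0.25³ + 0.25⁴ + 0.25⁵ + 2 × 0.25⁶ = 0.3335. The Day 240/Day 180 ratio with F = 0.7 and ka 0.15 is 0.3256/0.3335 = 0.98. With F = 1 and ka 2.0 it is (1.0237 × 0.3125 + 0.0208)/0.3335 = 1.02. Nearly the same ratio thus arises from bioavailabilities 30% apart. With F = 1 the ratio runs from 1.02 (ka 2.0) to about 1.37 (ka 0.15).

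**The case against.** The plan's wording is softer than a firm promise. The parameters are introduced as examples, reporting depends on the look of the fits, and individual values are named only for CL and V. Because the list is illustrative, the absence of bioavailability from it does not show that the model would omit it. All of this stands as a reading of the text. None of it fixes ka, adds an absorption-phase sample or tests identifiability, and the population ka remains a named output.

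Three stronger readings are tempting, and the documents do not support them.

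- A reader might infer that ka cannot be identified at all. Troughs do move with ka. With bioavailability known and absorption slow relative to a short half-life, mean ka could be estimated with an RSE of about 16-20%. The failure is practical, and it is complete only for the variance.
- A reader might take absorption to be complete by the time of the trough. The documents give no ka. The fraction unabsorbed at 30 days is e^(-30ka): about 1% at ka 0.15 and 5% at ka 0.1. At ka 0.1 the steady-state shift at a 15-day half-life would be +33%, so the results depend on the assumed lower bound.
- A reader might expect a poorly informed ka to distort CL and V. Nothing shows this. IV-phase samples run from Day 7 to Day 180, and the RSEs of CL and V stay near 10-12% whether bioavailability is known or estimated.

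The study is also exploratory and, by Section 8.1, not powered for statistical analysis. No decision rule uses ka. This limits the importance of the point but does not answer it.

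**Conclusion.** The point holds in a limited form, and Section 8.5.3 is wrong as written on ka. At most 20 SC-phase troughs, possibly none, cannot deliver a between-patient variance of ka: its RSE is at least 118% in every scenario tried, all of them with every patient switching. Mean ka is weakly informed and practically confounded with bioavailability. CL and V are unaffected in substance.

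The sample count comes from the documents alone. The sizes rest on assumed values: half-life 15-30 days and ka 0.15-2.0 per day for the trough shifts, and the wider half-life and variance assumptions listed above for the precision figures. The severity is minor: a stated secondary output that the design cannot support, with no bearing on the primary endpoint, on safety or on any treatment rule.

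**What to change.** Reword Section 8.5.3 as follows:

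- Report CL and V, with their between-patient variances, as the estimated parameters.
- Remove the random effect on ka. Fix ka at a pre-specified external value, with its source stated, and repeat the fit over a stated sensitivity range. If few patients switch, limit the model to the IV data.
- State how bioavailability is handled.
- Report any comparison of the Day 180 IV trough with the Day 240 and Day 360 SC troughs descriptively, as a trough ratio. If it is expressed as relative SC exposure, state that it is conditional on the assumed ka and show it across the sensitivity range, because the ratio alone does not separate the two.

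The cost is SAP wording only, with no new samples. The loss is a study-specific ka. Extra absorption-phase sampling would be the dearer route and only a partial one. As an illustration, four samples in the 14 days after one SC dose would bring the RSE of mean ka to about 12-36% with 10 switchers, but that of its variance would still be about 67-675%. The random effect should therefore go in either case.

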## **8.6 Interim analyses**

There will be statistical analysis at Day 30 , Day 90, Day 180 and Day 360.

## **8.7 Sample size calculation**

Because of exploratory nature of the study, 10 patients will provide information.

# **9 Ethical considerations**

## **9.1 Regulatory and ethical compliance**

This clinical study was designed and shall be implemented and reported in accordance with the ICH Harmonized Tripartite Guidelines for Good Clinical Practice, with applicable local regulations (including European Directive 2001/20/EC, US Code of Federal Regulations Title 21, and with the ethical principles laid down in the Declaration of Helsinki.

## **9.2 Informed consent procedures**

Eligible patients may only be included in the study after providing written (witnessed, where required by law or regulation), IRB/IEC-approved informed consent, or, if incapable of doing so, after such consent has been provided by a legally acceptable representative of the patient. In cases where the patient's representative gives consent, the patient should be informed about the study to the extent possible given his/her understanding. If the patient is capable of doing so, he/she should indicate assent by personally signing and dating the written informed consent document or a separate assent form. Informed consent must be obtained before conducting any study-specific procedures (i.e. all of the procedures described in the protocol). The process of obtaining informed consent should be documented in the patient source documents.

Novartis will provide to investigators in a separate document a proposed informed consent form that complies with the ICH GCP guideline and regulatory requirements and is considered appropriate for this study. Any changes to the proposed consent form suggested by the investigator must be agreed to by Novartis before submission to the HA/EC, and a copy of the approved version must be provided to the Novartis monitor after HA/EC approval.

Women of child bearing potential should be informed that taking the study treatment may involve unknown risks to the fetus if pregnancy were to occur during the study and agree that in order to participate in the study they must adhere to the contraception requirement for the duration of the study. If there is any question that the patient will not reliably comply, they should not be entered in the study.

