## 5.7 Patient demographics/other baseline characteristics

Patient demographic and baseline characteristic data to be collected on all patients include: date of birth, age, sex, ethnicity, patient referral source, relevant medical history/current medical condition present before signing informed consent. Where possible, diagnoses will be recorded, not symptoms.

Subjects should be seen for all post-baseline visits on the designated day with the allowance of a  $\pm 7$  day window for all visits. Subjects who discontinue study drug before completing the study, and those who prematurely withdraw from the study for any reason, should be scheduled for a visit 8 weeks ( $\pm 1$  week) after their last infusion /injection, at which time all of the assessments listed for the final visit will be performed.

Subjects who discontinue study drug also should return for a last assessment. If they refuse to return for this or are unable to do so, every effort should be made to contact them or a knowledgeable informant by telephone to determine the reason for discontinuation. At a minimum, they will be contacted for safety evaluations during the 30 days following the last dose of study drug, including final contact at the 30-day point. Documentation of attempts to contact the patient should be recorded in the patient record.

Information that will be collected on subjects who are screened but not enrolled includes patient demographics (age, gender, and ethnicity) and primary reason for not continuing.

If a patient discontinues before entering Visit 1, only the demographic information and Screening Log entry with the primary reason for discontinuation should be completed on the CRF. It is not necessary to complete all the required evaluations at the time of discontinuation unless medically indicated.

At screening visit information on age, sex, will be collected. Relevant medical history/current medical conditions, family medical history, will be recorded on the respective CRF page. The following should be recorded on the respective CRF page.

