### 5.10.5 Pregnancy and assessments of fertility

Canakinumab should not be given to pregnant women. Female subjects of child-bearing potential must undergo pregnancy testing throughout the study and need to agree to an effective method of contraception during the entire study and for at least 3 months after study completion. **Serum test and/or urine test are mandatory for pregnancy at the screening visit for woman .** Other assessments

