## 6.2 Serious adverse events

### 6.2.1 Definition of SAE

An SAE is any adverse event (appearance of (or worsening of any pre-existing) undesirable sign(s), symptom(s) or medical condition(s) which meets any one of the following criteria

- is fatal or life-threatening
- results in persistent or significant disability/incapacity
- constitutes a congenital anomaly/birth defect
- requires inpatient hospitalization or prolongation of existing hospitalization, unless hospitalization is for :
  - routine treatment or monitoring of the studied indication, not associated with any deterioration in condition
  - elective or pre-planned treatment for a pre-existing condition that is unrelated to the indication under study and has not worsened since signing the informed consent
  - treatment on an emergency outpatient basis for an event not fulfilling any of the definitions of a SAE given above and not resulting in hospital admission
  - social reasons and respite care in the absence of any deterioration in the patient's general condition
- is medically significant, i.e. defined as an event that jeopardizes the patient or may require medical or surgical intervention to prevent one of the outcomes listed above.

All malignant neoplasms will be assessed as serious under “medically significant” if other seriousness criteria are not met.

**Unlike routine safety assessments, SAEs are monitored continuously and have special reporting requirements; see Section 7.2.**

All adverse events should be treated appropriately. Treatment may include one or more of the following: no action taken (i.e. further observation only); [study/investigational] (*select*) treatment dosage adjusted/temporarily interrupted; study drug(s) permanently discontinued; concomitant medication given; non-drug therapy given. The action taken to treat the adverse event should be recorded on the Adverse Event CRF.

Once an adverse event is detected, it should be followed until its resolution or until it is judged to be permanent, and assessment should be made at each visit (or more frequently, if

necessary) of any changes in severity, the suspected relationship to the investigational treatment, the interventions required to treat it, and the outcome.

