### **6.2.2 SAE reporting**

To ensure patient safety, every SAE, regardless of causality, occurring after the patient has provided informed consent and until 30 days *following the last administration of study treatment* must be reported to Novartis within 24 hours of learning of its occurrence. Any SAEs experienced after the 30 days period should only be reported to Novartis if the investigator suspects a causal relationship to study treatment.

Recurrent episodes, complications, or progression of the initial SAE must be reported as follow-up to the original episode, regardless of when the event occurs. This report must be submitted within 24 hours of the investigator receiving the follow-up information. An SAE that is considered completely unrelated to a previously reported one should be reported separately as a new event.

Information about all SAEs (*either initial or follow up information*) is collected and recorded on the paper Serious Adverse Event Report Form. The investigator must assess the relationship to *each specific component of study treatment (if study treatment consists of several drugs)* complete the SAE Report Form in English, and send the completed, signed form by fax within 24 hours after awareness of the SAE to the local Novartis Drug Safety and Epidemiology Department. The telephone and fax number of the contact persons in the local department of Drug Safety and Epidemiology, specific to the site, are listed in the investigator folder provided to each site. The original copy of the SAE Report Form and the fax confirmation sheet must be kept with the case report form documentation at the study site. Follow-up information should be provided using a new paper SAE Report Form stating that this is a follow-up to a previously reported SAE

Follow-up information provided should describe whether the event has resolved or continues, if and how it was treated, whether the treatment code was broken or not and whether the patient continued or withdrew from study participation. Each re-occurrence, complication, or progression of the original event should be reported as a follow-up to that event regardless of when it occurs.

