### **6.3 Pregnancy reporting**

To ensure patient safety, each pregnancy occurring while the patient is on study treatment must be reported to Novartis within 24 hours of learning of its occurrence. The pregnancy should be followed up to determine outcome, including spontaneous or voluntary termination, details of the birth, and the presence or absence of any birth defects, congenital abnormalities, or maternal and/or newborn complications.

Pregnancy should be recorded on a Clinical Trial Pregnancy Form and reported by the investigator to the local Novartis Drug Safety and Epidemiology Department. Pregnancy follow-up should be recorded on the same form and should include an assessment of the possible relationship to the [investigational/study treatment] (*select*)

Any SAE experienced during pregnancy must be reported on the SAE Report Form.

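### Consent wording (9.2) and mandatory pregnancy reporting (6.3) both stop short of the contraception period that 5.10.5 requires

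*Combined protocol and SAP*

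**What the plan says.** Four parts of the protocol bear on this.

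- **Contraception (5.10.5).** Canakinumab is not to be given in pregnancy. Women of child-bearing potential are tested for pregnancy and must agree to effective contraception "during the entire study and for at least 3 months after study completion".
- **Consent (9.2).** Women are to be told of "unknown risks to the fetus if pregnancy were to occur during the study" and to agree that "they must adhere to the contraception requirement for the duration of the study". The consent form is a separate document.
- **Pregnancy reporting (6.3).** The rule is that "each pregnancy occurring while the patient is on study treatment must be reported" to the sponsor within 24 hours of the site learning of it, with follow-up to outcome. The section adds: "Any SAE experienced during pregnancy must be reported on the SAE Report Form".
- **Later safety events (6.2.1, 6.2.2, 5.7).** An event that "constitutes a congenital anomaly/birth defect" is serious. All serious events are reportable up to 30 days after the last dose. After that: "Any SAEs experienced after the 30 days period should only be reported to Novartis if the investigator suspects a causal relationship to study treatment". The end of 6.2.1 also has investigators instruct patients to report later events that they or their own physician think may be related to treatment; those that are serious go to the sponsor. Under 5.7, patients who stop early should attend a visit 8 weeks (±1 week) after the last dose. Those who cannot or will not return are, at a minimum, "contacted for safety evaluations during the 30 days following the last dose of study drug".

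**The concern.** The protocol sets its own period of caution, the study plus at least 3 months, and then does not carry it into two sections that depend on it. In 9.2, both the agreement and the risk information are worded for the study alone. In 6.3, the duty to report and follow a pregnancy ends with treatment.

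Two things are at stake. The first is consistency: if the consent form were drafted from 9.2 alone, it could state a shorter period than 5.10.5 requires. The second is safety information. A woman could conceive while the protocol still asks her to avoid pregnancy, and nothing would oblige the site to report the pregnancy or follow it to outcome. Safety is part of the primary objective, and section 7.4 states that no data monitoring committee is required, so the written reporting rules carry more weight.

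**Working it through.** The plan gives no figure for this gap, so there is none to reproduce. The check compares the periods on one timeline.

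**Inputs**
- Months are taken as 30 days, which matches the spacing of the monthly visits in Table 5-1.
- Final scheduled visit: Day 360 (Table 5-1). This is taken as study completion for completers.
- Last dose, reading A: Day 360. Table 5-1 marks drug administration at Visit 15, and 5.10.7 describes the Day 360 sample as taken before dosing.
- Last dose, reading B: Day 330. The text of 3.1 gives 1 initial dose, 5 monthly doses and 6 further monthly doses, so 1 + 5 + 6 = 12 doses. Starting on Day 0, the twelfth falls on Day 11 × 30 = 330.
- End of treatment for 6.3 is not defined. It is taken either as the last dose or as one 30-day dosing interval later.

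**Completers**

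End of the contraception period = 360 + 3 × 30 = Day 450.

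Days without a mandatory pregnancy report = 450 − end of treatment.

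Days of that also beyond the 30-day window for serious adverse events = 450 − the later of (end of treatment, last dose + 30).

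| Last dose | End of treatment | Days without mandatory report | Of which beyond the 30-day window |
|---|---|---|---|
| 330 | 330 | 450 − 330 = 120 | 450 − 360 = 90 |
| 330 | 360 | 450 − 360 = 90 | 450 − 360 = 90 |
| 360 | 360 | 450 − 360 = 90 | 450 − 390 = 60 |
| 360 | 390 | 450 − 390 = 60 | 450 − 390 = 60 |

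The range for completers is 60 to 120 days, of which 60 to 90 lie beyond the 30-day window.

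**Early leavers**

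Section 5.10.5 counts from study completion, which is not defined for someone who leaves early. Under 3.1 this includes non-responders dropped at month 1 after a single dose. If completion is the 8-week visit in 5.7, the period ends 8 × 7 + 90 = 56 + 90 = 146 days after the last dose. If treatment is taken to end 30 days after that dose, 146 − 30 = 116 days remain without a mandatory report. Both figures fall if completion is set earlier.

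**Do other rules close the gap?**
- A birth defect is a serious adverse event, but delivery after a post-treatment conception would normally fall well past 30 days from the last dose. The sponsor would then hear of it if the investigator suspects causality (6.2.2), or through a patient who reports it as possibly related (end of 6.2.1).
- Both routes start from a suspected adverse event. An uncomplicated pregnancy is not clearly one, and neither route calls for follow-up to outcome.
- The 8-week visit may bring a pregnancy to light, but 6.3 would not require a report of one that began after treatment.

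No other section extends the 9.2 wording or the 6.3 duty to the 3 months.

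**The case against.** The strongest reply is that the 3-month agreement is already mandatory. Section 5.10.5 requires the patient's own agreement, 9.3 binds investigators to every protocol instruction, and 9.2 refers back to the contraception requirement, which can be read as the one in 5.10.5. The consent form is separate and is reviewed by the ethics committee together with the protocol. All of this stands. A reader might infer from 9.2 that women are told a shorter period than the protocol requires. The documents do not support that: the form is not available and may already give the 3 months. What remains is that both clauses in 9.2 carry a limit that 5.10.5 does not.

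A reader might also infer that late birth defects go unreported, or that patients who stop early are out of contact after 30 days. Neither follows. Late birth defects have the two routes shown above, one of which can be triggered by the patient or her own physician. For early leavers the default is the 8-week visit, and 30-day contact is the stated minimum for those who do not return.

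Finally, nothing in the protocol says that the reporting window must equal the contraception window, so 6.3 does not contradict 5.10.5. That is fair, and extending 6.3 is an improvement more than a correction. It is still a sensible one, because the sponsor chose the 3 months and the present rule leaves a pregnancy in that time without a mandatory report.

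**Conclusion.** The point holds as a minor one. Section 9.2 is inconsistent with 5.10.5 and should be harmonised. Section 6.3 leaves an uncomplicated pregnancy that begins after treatment, but inside the required contraception period, with no mandatory report or follow-up to outcome.

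For completers the uncovered period is about 60 to 120 days. This assumes 30-day months, completion at Day 360, a last dose on Day 330 or Day 360, and treatment ending at the last dose or 30 days later. For early leavers it cannot be fixed from the text; it is about 146 days from the last dose if completion is the 8-week visit. About 10 patients are planned and the number of women is not stated, so the number affected cannot be given. No sample size, endpoint or statistical analysis is affected.

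**What to change.** 1. **9.2:** extend both the contraception agreement and the fetal-risk statement to cover the 3 months after completion that 5.10.5 sets, and check that the consent form says the same.
2. **6.3:** require any pregnancy that occurs on treatment, or within the 5.10.5 contraception period, to be reported within 24 hours of the site learning of it and followed to outcome.
3. **5.10.5:** state when the contraception period ends for patients who leave early, for example by counting from a named visit or from the last dose.

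The cost is one written amendment under 10.1, a check of the consent form, and a few more months of pregnancy reporting for the women among about 10 patients. It needs no extra visits or tests and no change to the analysis.
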